It is known that MAT of OUD with BUP is associated with decreased risk of opioid overdose, improved engagement in treatment at 30 days, and less self-reported opioid use compared with those who receive only a brief negotiated interview (BNI) or referral for counselling.^{11,12} As a result of this previous research at our institutions, patients in our ED who are successfully resuscitated with naloxone following an opioid overdose are routinely screened using the Mini International Neuropsychiatric Interview (MINI)^{13,14} for OUD. Those who screen positive for moderate to severe OUD are offered initiation of BUP treatment in the ED, with outpatient primary care clinic referral for ongoing medical monitoring and treatment. At the time of the ED visit, however, fewer than half of these patients will consent to initiation of BUP.¹⁵ Those who decline are offered overdose education and naloxone (OEN) by ED staff. A safety net that includes tailored linkage plans to effectively engage opioid overdose survivors with BUP, intensive psychosocial support, and follow-up counseling in the community is needed. To gain a better understanding of the motivations of those who decline the offer of BUP, we have purposively sampled 16 opioid overdose survivors who agreed to participate in a qualitative research study looking at their knowledge and understanding of OUD (unpublished). Predominant themes included the following: ambivalence regarding the effectiveness of treatment for OUD, concerns about concurrent social supports such as housing and mental health services; lack of appreciation for the risks associated with OUD (even with multiple prior overdoses); strong, but abstract desire to discontinue use of opioids, despite refusal of treatment; and limited understanding of how to prevent or emergently manage overdoses. These perceptions from the patient population with OUD declining treatment directly informed our proposed research strategy, which connects affected participants with community resources such as treatment with BUP.

Peer support and recovery in OUD.

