There has been extensive prior literature comparing treatment modalities for patients with OUD. In these studies, the arms are rigidly controlled to assess efficacy of the treatments. While BUP is currently considered the most effective treatment, many patients decline to start it after an overdose, and a substantial proportion of those who do start it do not achieve remission of their OUD. Less than half of patients who start it remain engaged in treatment at the time of follow up, though the proportion still engaged in treatment with BUP is roughly double that of the patients who are treated only with BNI or community referral. Investigators both here and in large, multicenter trials have found that outcomes of BUP therapy were not substantially improved by the addition of adjunctive counselling or cognitive behavioral therapy.³¹⁻³³ Adjunctive counselling was not shown to improve outcomes of patients on BUP in any of these studies. It should be noted, however, that the counselling was scripted and manual-driven to ensure consistency. Further, in one of the reports,³³ all patients were tapered off the BUP during the study with a predictable high relapse rate. Our study will demonstrate whether a more patient-centered approach, combining motivation to treatment while providing connections to continuous, community-based medical and psychosocial support, can improve outcomes compared with historical and concurrent controls. Positive findings in this study will further broaden the potential scope of mobile integrated health care, an emerging aspect of EMS. It may also reveal a synergistic effect of the traditionally community-oriented recovery model using peer coaches with the best medical management. If we find that our cohort of patients managed through this collaborative approach has improved outcomes, studies in the field will become even more complex, as it will be clear that interventions probably cannot be compared in isolation, but will be carried out with customized and adaptable supportive care.

Innovation.

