
- d. For multi-site studies for which the Yale PI serves as the lead investigator: N/A
 - i. How will adverse events and unanticipated problems involving risks to subjects or others be reported, reviewed and managed? N/A
 - ii. What provisions are in place for management of interim results? N/A
 - iii. What will the multi-site process be for protocol modifications? N/A

12. **Statistical Considerations:** Describe the statistical analyses that support the study design.

Study design

Primary outcomes

The primary outcomes will be 1) percentage of individuals with repeat opioid overdose events requiring naloxone resuscitation, identified using YNHH's electronic medical record system (EPIC), and 2) percentage of individuals engaged in any treatment for OUD or who are in remission. Data will be recorded at baseline and at 30 and 180 days after consent to participate in the research.

Secondary outcomes

The secondary outcomes will be 1) frequency and percentage of individuals with positive opioid tests (urine) recorded in their hospital charts or during medication program monitoring, and 2) frequency and percentage of subjects with self-reported opioid use. Data will be recorded at baseline and at 30 and 180 days after consent to participate in the research.

Statistical analyses

We will document demographics (sex, race/ethnicity, age, education, employment status, etc.) and clinical characteristics (e.g., heroin use, non-opioid use in the past 6 months, lifetime treatment for addiction etc.) among all cohorts. χ^2 tests (2 df) will be employed to detect statistically significant differences.

Group	X	No X	Total
PRIDE + CCAR intervention			
BUP-initiated in ED after OD			
Historical control(s)			
Total			

For primary outcomes, "X" is % of repeated overdose events or % of treatment engagement. For secondary outcomes, "X" is frequency or % positive testing for opioid tests or % (self-reported) opioid abuse.

Sample size determination

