We estimate that data from approximately 100 individuals will be used. Recent data from American Medical Response (AMR) suggest that in 2017, 447 individuals have been transported to the YNHH ED for heroin overdose, and 136 others were documented as being treated in the ED. We expect that many of these individuals will elect to undergo BUP treatment in the ED, but that many others will enroll in our research. However, inevitably some will be lost to follow up. Power calculations are based on previously published data involving screening, brief intervention, and referral to treatment and the use of buprenorphine in primary care settings.^{1,32,43} Findings suggest small-to-moderate ($f=0.2-0.4$) and moderate ($f=0.5$), respectively, effect sizes for these practices. Statistical power ($1-\beta$) will be 80%, and significance level (α) will be 5%.

SECTION II: RESEARCH INVOLVING DRUGS, BIOLOGICS, RADIOTRACERS, PLACEBOS AND DEVICES

If this section (or one of its parts, A or B) is not applicable, check off N/A and delete the rest of the section.

A. RADIOTRACERS

N/A

1. Name of the radiotracer: *Write here*
2. Is the radiotracer FDA approved? YES NO

If NO, an FDA issued IND is required for the investigational use unless RDRC assumes oversight.

3. Check one: IND# *Write here* or RDRC oversight (RDRC approval will be required prior to use)
4. **Background Information:** Provide a description of previous human use, known risks, and data addressing dosage(s), interval(s), route(s) of administration, and any other factors that might influence risks. If this is the first time this radiotracer is being administered to humans, include relevant data on animal models.
Write here
4. **Source:** Identify the source of the radiotracer to be used. *Write here*
5. **Storage, Preparation and Use:** Describe the method of storage, preparation, stability information, method of sterilization and method of testing sterility and pyrogenicity.
Write here

B. DRUGS/BIOLOGICS

N/A

1. If an **exemption from IND filing requirements** is sought for a clinical investigation of a drug product that is lawfully marketed in the United States, review the following categories and complete the category that applies (and delete the inapplicable categories):

Exempt Category 1: The clinical investigation of a drug product that is lawfully marketed in the United States can be exempt from IND regulations if all of the following are yes:	

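### Improvement over the concurrent controls is a poor test of the RCP programme, because those controls accepted buprenorphine and the plan's own premises put them ahead

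*Combined protocol and SAP*

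**What the plan says.** The Background (item 3, under how the project will improve scientific knowledge) says the study will show whether a patient-centred approach "can improve outcomes compared with historical and concurrent controls". The hypotheses in the opening aims and in the Research Plan (item 4) are directional, with fewer overdoses and more remission, but name no comparator.

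The aims, the Research Plan and the table in Statistical Considerations (item 12) define the comparators. One row is "BUP-initiated in ED after OD". Another is historical controls, who according to the aims received printed resources only. RCP participants must have refused BUP if it was offered (item 7, criterion 16) and must not be stably enrolled in medication-assisted treatment at consent (criterion 14).

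On the effect of BUP, the Background says that "MAT of OUD with BUP is associated with decreased risk of opioid overdose". It calls BUP the most effective current treatment, says that fewer than half of those who start it remain engaged, and adds that "the proportion still engaged in treatment with BUP is roughly double that of the patients who are treated only with BNI or community referral". It also says that "Adjunctive counselling was not shown to improve outcomes of patients on BUP in any of these studies".

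The second primary outcome is engagement in any treatment for opioid use disorder, or remission. Daily medication-assisted treatment by itself counts as remission. The analysis is a chi-square with 2 df across the three groups, with no pairwise contrast, direction or margin.

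**The concern.** The two control groups sit on opposite sides of where the RCP cohort can be expected to fall. The historical group had no BUP. The concurrent group accepted BUP at the index visit, and while they stay on it they meet the engagement outcome. The RCP cohort starts off BUP and consists largely of people who turned it down. A comparison with BUP starters therefore mixes the effect of RCP with the effect of BUP and with willingness to be treated.

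Two misreadings follow. A programme that helps refusers could be reported as no better than its concurrent control, or as worse. And a significant three-group test could be credited to RCP when the BUP row alone produced it. The plan gives the BUP row no stated role, such as benchmark, non-inferiority with a margin, or superiority, so nothing in it guards against either.

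**Working it through.** **The plan's own figure.** Sample size determination gives about 100 individuals, 80% power, 5% significance and effect sizes of f = 0.2–0.4 and 0.5. Treating these as the chi-square effect size w, a 2-df test needs a total of 241 (w = 0.2), 108 (0.3), 61 (0.4) or 39 (0.5). A total of 100 corresponds to w = 0.31. The stated range brackets 100, but no stated value yields it, so the figure is neither reproduced nor shown to be wrong. The point below does not depend on it.

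**Inputs.**
- Engagement with BUP: fewer than half (Background). 50% is taken as the upper limit; 40–49% is checked below.
- Engagement without BUP: half of that, so 25%. The stated ratio is for BUP against brief interview or referral. Applying it to BUP refusers and to the historical group is an assumption.
- Group sizes: not given for the controls, and the 100 may be the RCP group alone (Section III targets 100 participants) or all groups together. Both 33 and 100 per row are shown.
- Pairwise checks: two-sided pooled z tests at 5%, by exact binomial enumeration. The plan specifies no pairwise test, so this too is an assumption.

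**Break-even.** 50% / 25% = 2, so RCP must double engagement among refusers to tie with the BUP row.

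**RCP works by moving refusers onto BUP, with the same retention.** With uptake x, RCP rate = 0.50x + 0.25(1 − x). At x = 0.6 this is 0.30 + 0.10 = 40%, a true gain of 15 points. At x = 0.8 it is 0.40 + 0.05 = 45%.

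| Uptake | RCP rate | Per row | Sig. better than BUP | Sig. worse than BUP |
|---|---|---|---|---|
| 60% | 40% | 33 | 0.4% | 15% |
| 60% | 40% | 100 | 0.04% | 31% |
| 80% | 45% | 100 | 0.4% | 11% |
| 100% | 50% | 100 | 2.8% | 2.8% |

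At 100 per row, RCP is significantly better than the 25% group in 63% of trials at 60% uptake and 85% at 80% uptake.

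**Sensitivity to the BUP rate.** With BUP at 40–49%, the non-BUP rate at half of that, and RCP closing half the gap, RCP is significantly better than BUP in at most 0.3% of trials. Its point estimate lies below BUP in 77–95%.

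**RCP retains people better than BUP starters are retained.** At 80% uptake, with the remainder at 25%, the tie requires 0.8r + 0.05 = 0.50, so r = 56%. At 60% uptake, 0.6r + 0.10 = 0.50 gives r = 67%. With 80% uptake and 70% retention, the RCP rate is 0.56 + 0.05 = 61%, and at 100 per row it is significantly better than a 50% BUP row in 36% of trials.

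**The planned 2-df test, RCP wholly ineffective (25% / 50% / 25%).** It is significant in about 59% of trials at 33 per row and 98% at 100, because of the BUP row alone. An effective RCP does not raise these chances. With BUP at 49% and non-BUP at 24.5%, the test is significant in 58% (33 per row) or 97% (100) when RCP does nothing, and in 45% or 91% when RCP closes half the gap.

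**Overdose outcome.** The documents give no rates, so nothing is computed. The direction of the argument is the same, because the Background links BUP to lower overdose risk.

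**The case against.** The strongest reply is that RCP could exceed the BUP row. The Background qualifies the negative counselling studies: the counselling was scripted, and one study tapered all patients off BUP. It raises a possible synergy between peer coaching and the best medical management, and the Innovation paragraphs say the combination has not been studied formally. Methadone, intensive outpatient and residential care count as treatment, and a recovery capital score of at least 27.5 counts as remission. The uptake model is capped at the BUP rate, so its very small chances of superiority partly restate that cap. This stands. A reader might infer that RCP cannot beat BUP starters; the documents do not support that, as the 36% figure shows. But it takes high uptake together with retention above that of BUP starters, and the plan offers no data for either. Even a true 10-point advantage would be shown in only about 15% (33 per row) to 31% (100 per row) of trials.

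A reader might also infer that the plan predicts a win over BUP starters, or that missing one would be declared a failure. Neither is written. The Background asks whether outcomes can improve, the hypotheses name no comparator, there is no success rule, and RCP could still beat the historical row.

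Finally, because of the words about BUP being offered, some RCP participants may never have refused it. That softens the contrast between the groups but does not remove it.

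**Conclusion.** The point holds as a mismatch between the stated question and one of its two comparators. Under the plan's own premises the BUP row starts ahead. Unless RCP about doubles engagement among refusers, it will not match that row, and a real 15-point gain would appear significantly worse in 15% to 31% of trials and significantly better in under 0.5%. The single 2-df test cannot show what RCP did, since it is significant in about 59% to 98% of trials when RCP does nothing.

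These sizes rest on 50% and 25% engagement, 33 to 100 per row and, for the pairwise figures, 60% BUP uptake with unchanged retention. Higher uptake and better retention would reduce the problem. Lower engagement among refusers than among referred patients would increase it. For overdose the conclusion is qualitative only.

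**What to change.** 1. In the opening aims, the Background paragraph on scientific knowledge, the Research Plan and Statistical Considerations, name RCP versus the non-BUP comparator as the contrast that tests the hypothesis of improvement. In Statistical Considerations, say that this conclusion will not be drawn from the 2-df chi-square.
2. Describe RCP versus ED-started BUP as a benchmark. Report the difference with a 95% confidence interval for each of the two primary outcomes at 30 and 180 days, four intervals in all.
3. State how the benchmark will be read. The groups differ by acceptance of BUP and no margin is set, so a non-significant difference is not evidence of equivalence, and a lower RCP rate is not evidence that RCP is ineffective or harmful.

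The cost is wording in four places, one named contrast and four intervals, with no new patients or data. There are two downsides. The study gives up a formal superiority test against ED-started BUP. And its inference on improvement then rests on a non-concurrent historical control, which should be stated as a limitation.

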Our principal aim is to determine whether a novel biopsychosocial intervention following opioid overdose (OD) affects 1) the frequency of secondary opioid OD events and 2) the proportion of individuals who remain engaged in treatment for opioid use disorder (OUD) or are in remission at 30 days and at 180 days post consent. We define remission as engagement in daily medication-assisted therapy (MAT)—typically buprenorphine/naloxone (BUP) or methadone—and/or a recovery capital score of ≥ 27.5 .¹ Our intervention will connect individuals with important community resources that hopefully will facilitate progress toward long-term recovery. Specifically, we will link individuals with moderate-severe OUD, who have experienced at least 1 opioid OD requiring naloxone resuscitation but refused BUP treatment, if offered, with 1) treatment with BUP, 2) methadone maintenance, intensive outpatient, or residential treatments, or 3) education materials from the Connecticut Community for Addiction Recovery (CCAR). Enrolled participants may switch from 1)-3) throughout. To carry out the intervention, an addiction recovery coach from CCAR and a health educator (research) paramedic will form a team (RCP team) and perform remote (including over-the-phone) and/or electronic follow-up visits after a participant has experienced at least 1 opioid OD requiring naloxone resuscitation. Our hypothesis is that the intervention, by the RCP team, connecting participants to community resources will decrease subsequent OD events and increase the likelihood of remission. To evaluate this hypothesis, data will be collected from self-report and from EPIC, Yale New Haven Hospital's (YNHH) medical record system. If the sources of information appear to conflict, then what is entered in EPIC will take precedence.

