To date, there is no standard of care for individuals with OUD who have overdosed on opioids, have been resuscitated by naloxone, and have refused BUP treatment. As noted in the previous section, YNHH typically will send home these individuals with OEN kits. However, follow-up care remains variable. Hence, we seek to determine whether individuals with OUD might benefit significantly from a novel, team-based intervention encouraging biopsychosocial and medical interventions. Our intervention will connect participants with important community resources that we expect will facilitate progress toward long-term recovery. Specifically, we will link individuals with moderate-severe OUD, who have experienced at least 1 opioid OD requiring naloxone resuscitation but who refused BUP treatment in the ED, if offered, with 1) treatment with BUP, 2) methadone maintenance, intensive outpatient, and/or residential treatment, or 3) education materials from CCAR. Enrolled participants may switch from 1)-3) throughout.

We wish to assess whether our intervention connecting participants to community resources affects 1) the frequency of secondary opioid OD events and 2) the proportion of individuals who remain engaged in treatment for OUD or are in remission at 30 days and at 180 days post consent. We define remission as engagement in daily medication-assisted MAT—typically BUP or methadone—and/or a recovery capital score of ≥ 27.5 . Our hypothesis is that the intervention by the RCP team will decrease subsequent OD events and increase the likelihood of remission. We also seek to determine whether the intervention affects 1) the frequency of positive-urine tests for opioids and 2) the frequency and proportion of subjects self-reporting opioid use. Our hypothesis is that our intervention will decrease both.

We will conduct our study as follows (Figures 1 & 2 below):

To prepare for the intervention, health educator paramedics and key study staff are required to attend 12 hours of in-person training, which is to take place over at least 2 days, to learn about best practices assessing those with OUD. [name], co-PI of this study, along with CCAR staff, will teach. Sessions will include training to conduct a brief negotiation interview (BNI) and a brief assessment of recovery capital (BARC-10) interview. Training also will prepare all staff to respectfully ask questions about potential overdose events and the possibility of creating and/or implementing a wellness plan.

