After resuscitation from opioid overdose by naloxone, affected individuals in the EDs at the York St. and Chapel St. campuses of YNHH will be screened for OUD using a MINI. As noted above, this is an evidence-supported, standard practice at our institution. Upon screening positive for OUD, individuals should be offered BUP treatment by staff. Those who screen positive for OUD, but who decline BUP, are offered overdose and naloxone kits. In addition, by using EPIC from the Department of Emergency Medicine / EMS

[figure not shown]
offices at [name], our study team will screen for resuscitated, OUD-positive individuals, who refused BUP, if offered, and may approach these individuals in the ED to ask whether they might be interested in research participation. To be clear, due to limitations imposed by the coronavirus pandemic of 2020, as of 06/02/2020 our team will screen for prospective participants from the office at [name] and will only enter the ED to consent potentially eligible participants in person. If the prospective subject were to express interest in study participation, then the study team members would set up an appointment to meet remotely (by EPIC telehealth functions (if applicable), phone, Zoom 5.0, or other encrypted, HIPAA-compliant electronic modality) at a time of the prospective participant's choosing. Informed consent may be obtained by the RCP team in the ED or at the first electronic visit, although the latter is more likely given the constraints of ED accessibility at this time. In addition, ED providers and affiliates from AMR, staff from CCAR, Project ASSERT, Elm City Communications, and the Community Health Care Van may refer interested individuals to study participation, providing that at some time in the previous 7 days the prospective participant overdosed on opioids, were resuscitated by naloxone, and screened positive for OUD..

The RCP team will respect all safety precautions, especially those pertaining to the coronavirus pandemic, at all times. The team will respect social distancing and will don face coverings when using the office at [name]. Personal protective equipment (PPE)—masks, gloves, gowns, and sanitizers as required by ED protocol—will be worn whenever appropriate.. All individuals who might work in the ED will undergo training in proper use, including donning and doffing the designated PPE.

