3. Screen positive for OUD using mini international neuropsychiatric interview (MINI) (if applicable)	+	-
4. At least 1 opioid overdose requiring resuscitation by naloxone	+	-
5. Have a non-opioid overdose explanation for decreased level of consciousness, miosis, or decreased respiratory rate (if applicable)	-	+
6. Positive for OUD using a health questionnaire containing questions about prescription opioid and heroin use	+	-
7. Not in a critically ill state at the time of consent (e.g., not actively suicidal, psychotic, septic, and/or experiencing cardiac arrest)	+	-
8. 3.,4., & 6. (in this column) must have occurred within ≤ 7 days (inclusive) from date of consent if the prospective participant were immediately discharged from the emergency department (ED), floor, or other health care facility; consent may be obtained at any of these locations	+	-
9. Homicidal	-	+
10. Able to consent to program/study participation	+	-
11. Permanent residence is a long-term care/skilled nursing facility	-	+
12. Simultaneously enrolled in another study whose principal investigator (PI) or co-PI is a faculty member in the Department of Emergency Medicine	-	+
13. Prescribed opioids for acute pain, chronic pain, or palliative care without OUD	-	+
14. Stably enrolled in opioid agonist treatment or other medication-assisted therapy for OUD at the time of consent	-	+
15. In police custody or incarcerated (at the time of consent to participate or any known time after). (Parolees & those on probation may be eligible, but are NOT the target population and may be enrolled only incidentally .)	-	+
16. Refused buprenorphine/naloxone (BUP), if offered	+	-
17. Has a mailing address or P.O. box	+	-
18. Able to answer questions electronically/remotely (including by phone)	+	-

8. How will **eligibility** be determined, and by whom? *Write here*

In general, eligibility will be determined by the RCP team. ED and study staff may assist occasionally.

9. **Risks:** Describe the reasonably foreseeable risks, including risks to subject privacy, discomforts, or inconveniences associated with subjects participating in the research.

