Our research is funded by an R01 through the CDC, which no longer issues hardcopy Certificates of Confidentiality (CoCs). However, as noted above, per section 2012 of the 21st Century Cures Act, a CoC "automatically" has been issued by the agency.

<https://www.cdc.gov/od/science/integrity/confidentiality/applinst.htm>

SECTION V: POTENTIAL BENEFITS

Potential Benefits: Identify any benefits that may be reasonably expected to result from the research, either to the subject(s) or to society at large. (Payment of subjects is not considered a benefit in this context of the risk benefit assessment.)

Participants are expected to directly benefit from the educational, counseling, and medical resources and contacts. We expect that this will provide better outcomes in the short- and possibly long-terms.

SECTION VI: RESEARCH ALTERNATIVES AND ECONOMIC CONSIDERATIONS

1. **Alternatives:** What other alternatives are available to the study subjects outside of the research? Participants may decline study participation or participate in another study. BUP can be started in the ED for individuals willing to accept it at the time of an OD. Other resources for harm reduction and treatment are routinely provided at the time of an ED visit, but are seldom associated with positive short-term outcomes.

2. **Payments for Participation (Economic Considerations):** Describe any payments that will be made to subjects, the amount and schedule of payments, and the conditions for receiving this compensation.
Participants will receive 3 payments of \$25 (for a total of \$75) after consent and after the first and second meetings. Each payment is given as a \$25 gift card to Stop & Shop. Initial payments may be obtained upon consent in the ED; subsequent payments will be mailed or provided electronically, according to subjects' preferences.
3. **Costs for Participation (Economic Considerations):** Clearly describe the subject's costs associated with participation in the research, and the interventions or procedures of the study that will be provided at no cost to subjects.
The research will not generate any costs to participants, as we expect that study personnel will meet with them at settings and times of participants' choosing and convenience. All medical and laboratory testing is part of participants' routine care and is not directly a feature of the research itself. Additionally, for those electing to receive BUP, grant funding will cover its cost.

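### Primary outcome 1 counts repeat overdoses found in EPIC, so community reversals go uncounted, possibly more often in the RCP row; the plan should record kit issue and report such reversals separately.

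*Combined protocol and SAP*

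**What the plan says.** **Who is offered naloxone to take away.** Three statements describe this, each about people who decline BUP. Background (Section I, item 3): "Those who decline are offered overdose education and naloxone (OEN) by ED staff". Research Plan (item 4): "YNHH typically will send home these individuals with OEN kits", and again "Those who screen positive for OUD, but who decline BUP, are offered overdose and naloxone kits". The kits are ED usual care and not part of the study intervention.

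**Who enters the RCP cohort.** Criterion 16 in item 7 reads "Refused buprenorphine/naloxone (BUP), if offered". Referrals from ambulance staff, the recovery organisation, the housing authority and the health care van are also accepted.

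**How the outcome is found.** Under Primary outcomes in item 12, outcome 1 is the "percentage of individuals with repeat opioid overdose events requiring naloxone resuscitation, identified using" the hospital record system, EPIC. The statement of the principal aim at the start of the protocol is wider: "data will be collected from self-report and from EPIC". It adds that EPIC prevails if the two appear to conflict.

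**The comparators.** These are patients started on BUP in the ED over the same period, and historical controls described as having had printed material only. The plan does not say whether the BUP starters receive kits, or how overdoses were ascertained in the historical controls. Section VI, item 1 adds, without naming contents or recipients: "Other resources for harm reduction and treatment are routinely provided at the time of an ED visit".

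**The concern.** An overdose reversed by a bystander, with no hospital visit afterwards, fits the wording of the event but leaves no trace in EPIC. If this happened equally often in every row, the percentages would be too low but the risk ratio between rows would be undisturbed. The plan gives a reason to doubt that it does: take-home naloxone is described only for decliners, and declining BUP is the usual route into the RCP cohort.

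More missed events in the RCP row would lower its overdose percentage with no change in overdosing. That is the direction of the study hypothesis, on a primary outcome. As written, the plan cannot tell fewer overdoses from fewer hospital visits.

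**Working it through.** **The plan's own figures.** Item 12 gives no repeat-overdose rate and no capture rate, so there is no stated figure for this point to reproduce. Its one numerical target is about 100 individuals at 80% power and 5% significance, with effect sizes of 0.2-0.4 and 0.5. Read as Cohen's w in a chi-square test with 2 df, 0.2, 0.4 and 0.5 need 241, 61 and 39 in total; 100 corresponds to w of about 0.31, inside the stated range. Nothing below depends on this.

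**Inputs, all assumed.**
- True 180-day risk of a repeat overdose, p: 10-30%, the same in every row.
- Unrecorded share, m: 10-30%. Because the outcome is a percentage of people, m is the share of people with a repeat overdose whose events all stay out of EPIC.
- Row sizes are not given. Two cases are shown: 100 per row, and 33 per row (the planned 100 spread over three rows).

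**Bias in the risk ratio.** Observed risk = p × (1 − m). With equal true risks, the observed ratio is (1 − m in RCP) / (1 − m in comparator), whatever p and the sample size.

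| m in RCP | m in comparator | Spurious risk ratio |
|---|---|---|
| 10% | 0% | 0.90/1.00 = 0.90 |
| 20% | 0% | 0.80/1.00 = 0.80 |
| 30% | 0% | 0.70/1.00 = 0.70 |
| 30% | 10% | 0.70/0.90 = 0.78 |
| 30% | 20% | 0.70/0.80 = 0.875 |
| 30% | 30% | 0.70/0.70 = 1.00 |

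**Effect on the planned test.** Probability that the three-row chi-square test (2 df, 5%) rejects although true risks are equal, with losses in the RCP row only (noncentral chi-square):

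| p | Row size | m = 10% | m = 20% | m = 30% |
|---|---|---|---|---|
| 10% | 100 | 5.6% | 7.4% | 10.9% |
| 20% | 100 | 6.3% | 10.7% | 19.0% |
| 30% | 100 | 7.3% | 15.0% | 29.7% |
| 10% | 33 | 5.2% | 5.8% | 6.9% |
| 20% | 33 | 5.4% | 6.8% | 9.3% |
| 30% | 33 | 5.7% | 8.1% | 12.4% |

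If BUP starters lose the same share as RCP and historical controls lose none, the RCP/BUP ratio is 1.00. The three-row test can still reject through the historical row: 20.5% of the time at p = 20%, m = 30% and 100 per row.

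**The opposite error.** If reported reversals were added for RCP alone, so that RCP missed nothing while the comparator missed m, the ratio would be 1/(1 − m): 1/0.90 = 1.11 to 1/0.70 = 1.43. A one-sided count therefore cannot serve as the comparison.

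**The case against.** A reader might infer that the plan hands kits to RCP participants and not to BUP starters, so that missed events fall mainly in the RCP row and a favourable result would be the work of the kits. The documents do not support that.

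- The three statements say what decliners are offered; they do not say that starters get none. Section VI, item 1 describes harm-reduction resources as routine at ED visits, which may include starters.
- Kits are offered or typically provided, and uptake is unknown. Criterion 16 also admits people never offered BUP, and community referrals may have had no ED kit.
- EPIC is not the only source named: self-report is also collected for the principal aim. The Research Plan says staff are trained to ask about overdose events, though it ties this to no particular meeting. The Survey Tool and Handbook is not among the documents and may already hold a suitable question.
- The risks, unrecorded shares and row sizes above are assumptions.

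All of this stands, and it limits how firmly direction and size can be stated. It does not settle the matter. No rule says whether a reported reversal with no EPIC entry is a conflict that EPIC overrides, and item 12 read literally leaves it out. No interview is described for BUP starters, so self-report as planned could not be counted alike in the two concurrent rows.

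**Conclusion.** The point holds as a should-fix, not as a demonstrated bias. The documents establish that outcome 1 is identified in EPIC, that a community reversal without hospital contact would be missed, that kits are described only for decliners, and that the two statements on data sources are not reconciled.

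Under-counting may be larger in the RCP row and so favour the intervention. Against BUP starters this is unproven, because their kit receipt is not stated. Against historical controls the contrast in kits is better supported, but how their overdoses were found is not described.

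An excess loss of 10-30% in the RCP row gives a spurious risk ratio of 0.90-0.70, and equal loss gives 1.00. This range rests on assumed shares. The inflated rejection rates depend further on unstated row sizes and are small at 33 per row with modest losses.

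**What to change.** In item 12:

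1. Abstract kit issue at the index visit from EPIC for both the RCP and ED-BUP cohorts, and report it beside outcome 1. This settles the question the documents leave open.
2. Record at Meetings 1 and 2 any reversal without ED attendance. Reconcile the principal-aim statement with item 12 so that such a report, absent from EPIC, is not voided by EPIC precedence but is reported separately.
3. Keep the EPIC-identified comparison as the like-for-like analysis and label it *overdoses recorded in EPIC*. Add a supplementary RCP row (EPIC plus reported reversals).
4. Add a sensitivity analysis over the unrecorded share in each row: corrected ratio = observed ratio × (1 − m in comparator) / (1 − m in RCP). For example, an observed ratio of 0.80 becomes 0.80 × 1.00/0.80 = 1.00 if RCP loses 20% and the comparator none.

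Do not make the supplementary row a condition for claiming fewer overdoses. BUP starters are not interviewed, so that count is biased against RCP.

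The cost is one chart field, one interview item, one table row and a short sensitivity table. The downside is a more cautious conclusion on overdose frequency.
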